1.4 Analysis of the primary objective(s)

1.4.1 Variable

The primary variable is defined as the proportion of patients in whom a best overall response of complete (CR) or partial (PR) response or stable disease (SD) was observed at 16 weeks according to RECIST (version 1.0, [Therasse et al. 2000](#)) based on local radiologic assessments.

The best overall response for each patient was determined from the sequence of overall (lesion) responses at Visit 4/Week 8 and Visit 6/Week 16, respectively, according to the following rules (see Post-text supplement 1 to the study protocol):

- CR = at least two determinations of CR at least 4 weeks apart before progression.
- PR = at least two determinations of PR or better at least 4 weeks apart before progression (and not qualifying for a CR).
- SD = at least one SD assessment > 6 weeks after start of treatment (and not qualifying for CR or PR).
- PD = progression or death due to underlying cancer ≤ 16 weeks after start of treatment (and not qualifying for CR, PR or SD). Patients with symptoms of rapidly progressing disease without radiologic evidence will be classified as progression only when clear evidence of clinical deterioration is available and patient discontinued due to 'Disease progression'. Furthermore, patients without radiologic evidence for progression who were prematurely discontinuing from the study for 'unsatisfactory therapeutic effect', 'new cancer therapy' or 'death' (from any reason) will be classified as progression.
- UNK = all other cases (i.e. not qualifying for confirmed CR or PR and without SD after more than 6 weeks or early progression within the first 16 weeks)

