The best overall response is the best response recorded from the start of the treatment until disease progression/recurrence (taking as reference for PD the smallest measurements recorded since the treatment started). In general, the patient's best response assignment will depend on the achievement of both measurement and confirmation criteria.

To be assigned a status of PR or CR, changes in tumor measurements must be confirmed by repeat assessments that should be performed not less than 4 weeks after the criteria for response are first met.

The best overall response for each patient is determined from the sequence of overall (lesion) responses according to the following rules:

- CR = at least two determinations of CR at least 4 weeks apart before progression.
- PR = at least two determinations of PR or better at least 4 weeks apart before progression (and not qualifying for a CR).
- SD = at least one SD assessment > 6 weeks after start of treatment (and not qualifying for CR or PR).
- PD = progression or death due to underlying cancer ≤ 16 weeks after start of treatment (and not qualifying for CR, PR or SD). Patients with symptoms of rapidly progressing disease without radiologic evidence will be classified as progression only when clear evidence of clinical deterioration is available and patient discontinued due to ‘Disease progression’.
- UNK = all other cases (i.e. not qualifying for confirmed CR or PR and without SD after more than 6 weeks or early progression within the first 16 weeks)

Overall lesion responses of CR must stay the same until progression sets in, with the exception of a UNK status. A patient who had a CR can not subsequently have a lower status, e.g. PR or SD, as this would imply that one or more lesions reappeared, in which case the status would become a PD.

Overall lesion responses of PR must stay the same or improve over time until progression sets in, with the exception of a UNK status. However, if a patient has a PR ($\geq 30\%$ reduction of tumor burden compared to baseline) at one assessment, followed by a $< 30\%$ reduction from baseline at the next assessment (but not $> 20\%$ increase from previous smallest sum), the objective status at that assessment should be SD. Once a confirmed PR was seen, the overall lesion response should be considered PR (or UNK) until progression is documented.

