1.4.2 Statistical hypothesis, model, and method of analysis

The best overall response rate (CR/PR/SD/PD/UNK) was presented together with the appropriate two-sided confidence interval for the ITT set. Since the one-sided alpha was set to 10%, two-sided 80% confidence intervals were presented. Exact confidence intervals were computed according to the method of Clopper and Pearson.

The absolute number of patients showing a best overall response of CR, PR or SD was determined to conclude preliminary activity or non-activity of the study drugs in this patient population according to the rules outlined in CSP [section 10.2](#). Furthermore, the lower limit of the confidence interval was used to support the decision in favor of p_0 or p_1 : if the lower limit of the confidence interval overlapped p_0 , the hypothesis that p is greater than or equal to p_1 could be rejected; on the other side, if the lower limit of the confidence interval excluded p_0 , the hypothesis that p is greater than or equal to p_1 could be accepted.

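### A single unconfirmed PR or CR with no SD scan is scored as a failure in the primary count, while a single SD in the same position is a success

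*SAP*

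**What the plan says.** SAP 1.4.1 takes best overall response "from the sequence of overall (lesion) responses at Visit 4/Week 8 and Visit 6/Week 16, respectively". The categories, which repeat Protocol Post-text supplement 1, are:

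- PR: "PR = at least two determinations of PR or better at least 4 weeks apart before progression (and not qualifying for a CR"). CR likewise needs two determinations.
- SD: "SD = at least one SD assessment > 6 weeks after start of treatment (and not qualifying for CR or PR").
- PD: "PD = progression or death due to underlying cancer ≤ 16 weeks after start of treatment (and not qualifying for CR, PR or SD"). The SAP adds that patients without radiologic progression who stop early for unsatisfactory effect, new cancer therapy or death are also PD.
- UNK, the remainder: "UNK = all other cases (i.e. not qualifying for confirmed CR or PR and without SD after more than 6 weeks", and without early progression).

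SAP 1.4.2 sets the decision count: "The absolute number of patients showing a best overall response of CR, PR or SD was determined". PD and UNK are therefore failures, and both stay in the denominator.

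Protocol 10.4.1 defines the primary variable by the CR, PR or SD seen at 16 weeks under RECIST and states no confirmation requirement. When a PR loses its 30% reduction without progressing, Post-text supplement 1 says of the later scan that "the objective status at that assessment should be SD".

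**The concern.** The primary count measures disease control, so a better tumor result at a given scan should never score worse than a poorer one. The PR rule accepts PR or better, but the SD rule asks for an SD reading. A PR or CR that is not seen twice is neither a confirmed response nor an SD assessment. Unless the patient's other scan is SD, the response earns nothing.

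Only two scans feed the rule, so a response first seen at week 16 cannot be confirmed within the primary analysis. Later scans enter only the supportive analysis in SAP 1.4.4. At stake is the go/no-go count in arms I and II, where any loss of this kind pushes towards declaring the drug inactive. Arm III is to be summarized descriptively (Protocol section 10), so no decision there depends on it.

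**Working it through.** **Design figures first.** Inputs from SAP 1.6: p0 = 20%, p1 = 40%; arm I has 36 patients and a cut-off of 11 responders; arm II has 24 and a cut-off of 8. With X binomial(n, p):

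- Arm I: P(X ≥ 11 | 36, 0.20) = 0.0889; 1 − P(X ≥ 11 | 36, 0.40) = 0.0904.
- Arm II: P(X ≥ 8 | 24, 0.20) = 0.0892; 1 − P(X ≥ 8 | 24, 0.40) = 0.1919.

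These match the stated 8.9% and 9.0% (arm I) and 8.9% and 19.2% (arm II). The design arithmetic is sound.

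**Scoring rule.** Both scans fall after 6 weeks, so either can supply the SD assessment. They are 8 weeks apart, so the 4-week interval is met, and a confirmed response needs CR or PR at both. Applying SAP 1.4.1 literally to every sequence with exactly one PR, and then putting SD in place of that PR:

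| Week 8 / week 16 | Result | With SD in place of PR | Result |
|---|---|---|---|
| PR / SD | SD, success | SD / SD | SD, success |
| SD / PR | SD, success | SD / SD | SD, success |
| unknown / PR | UNK, failure | unknown / SD | SD, success |
| PR / unknown or missing | UNK*, failure | SD / unknown or missing | SD, success |
| PR / PD | PD†, failure | SD / PD | SD, success |

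*PD if the patient stopped for unsatisfactory effect, new cancer therapy or death. †UNK if the progression scan falls after 16 weeks. Both are still failures.

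Three of the five sequences are inverted. SD/PD succeeds because PD applies only to patients who do not already qualify for SD. A single CR behaves in the same way: unknown/CR, CR/unknown and CR/PD fail. If the SD rule is read as SD or better, exactly these sequences change to SD, and no others do.

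**Against Protocol 10.4.1.** In unknown/PR a PR is observed at 16 weeks, so the protocol definition gives success and the SAP gives failure. In PR/PD the patient has progressed at 16 weeks, so failure agrees with the protocol definition; the anomaly in that pair is the credit given to SD/PD. PR/missing has nothing observed at 16 weeks, so failure is defensible there too, and the anomaly is that SD/missing succeeds.

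**Size.** One patient is 1/36 = 2.8 percentage points in arm I and 1/24 = 4.2 in arm II. The documents give no frequency for the affected sequences. Let f be the assumed share of true successes lost. Power is then P(X ≥ cut-off | n, 0.40 × (1 − f)):

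| f (assumed) | Success rate after loss | Arm I power | Arm II power |
|---|---|---|---|
| 0% | 40% | 91.0% | 80.8% |
| 2.5% | 39% | 88.8% | 78.0% |
| 5% | 38% | 86.3% | 74.9% |
| 10% | 36% | 80.2% | 68.0% |

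**The case against.** A reader might infer that any patient responding at only one of the two scans is a failure. The documents do not support that. PR/SD and SD/PR both contain an SD assessment and count as successes, and the supplement codes a PR that fades without progressing as SD at the later scan. The problem is confined to a lone PR or CR with no SD scan.

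The remaining objections have force:

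- Two of the three inverted pairs are failures that agree with, or can be defended under, the definition at 16 weeks. Consistency could equally be reached by withdrawing credit from SD/PD. This stands, and that pair needs an explicit decision. It does not touch unknown/PR.
- SAP 1.4.3 says the derivation followed a sponsor guidance on response, which may deal with unconfirmed responses. Its content is not in the documents. The SAP's own UNK wording states the literal rule, so if the guidance says otherwise the SAP should say so.
- SAP 1.5.1 reports that no patient reached a best overall response of CR or PR. Under these rules that means confirmed responses; it does not exclude a lone PR, but nothing shows that one occurred.
- The chance of finishing exactly one responder short of the cut-off at a true rate of 40% (4.5% in arm I, 9.6% in arm II) might be read as the size of the defect. It is not. It holds under any scoring rule, and a changed decision also needs an affected patient.

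**Conclusion.** The point holds in its narrow form. As written in SAP 1.4.1 and Post-text supplement 1, a lone unconfirmed PR or CR without an SD scan is UNK or PD, while a lone SD in the same place is a success. For unknown/PR this contradicts Protocol 10.4.1, and the SAP's list of changes from the planned analysis does not mention it.

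The effect can only lower the count of successes. How many patients it touches is not known and may be none, so the documents do not support saying that either arm's conclusion was altered. The power losses rest on assumed values of f and on a literal reading of the rule. This is a small, cheap correction to the primary endpoint and does not affect the design.

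**What to change.** In SAP 1.4.1 and in Protocol Post-text supplement 1, redefine SD as one or more assessments of SD or better, more than 6 weeks after treatment start, in a patient who does not meet the CR or PR rule. Keep confirmation only for the CR and PR labels.

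State that PR/PD and SD/PD are scored the same way, and reconcile that pair with the 16-week definition in Protocol 10.4.1. The revised SD rule alone would make both successes, whereas status at 16 weeks would make both failures.

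List the change among the SAP's departures from the planned analysis, and report the primary count under both the existing and the revised rule.

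The cost is one reworded line in each document, a sentence on the PR/PD and SD/PD pair, and one extra count. The real downside is timing. The SAP already reports response results, and the revised SD rule on its own can only add successes, so it would be a late, data-aware change. That is why it has to be declared and both counts shown.

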1.4 Rationale

The systemic treatment of locally advanced or metastatic soft tissue sarcoma (STS) is unsatisfactory with few drugs showing signs of activity. Treatment is toxic, yet usually given with palliative intent.

PET responses and improvement of symptoms have been described in sarcoma patients with AP23573, an intravenous mTOR inhibitor () tested in a phase II trial (Sankhala et al., ASCO 2005, abstract 9028).

Recent data with this mTOR inhibitor AP23573 demonstrate a single-agent activity in a broad range of sarcoma tumor types in a phase I/II trial. In this trial the patients were enrolled according to their histological subtype of the tumor. Totally, 212 patients were enrolled of which over 90% had a progression at the time of study entry. 79% had 2 prior chemotherapies. The overall clinical benefit rate was 29% and the median OS was 40,1 weeks. In the subset of patients achieving a clinical benefit response, the OS was 67,6 weeks. (Chawla, ASCO 2007, abstract 10076).

The experiences with this mTOR inhibitor are a rational to test RAD001 in patients with soft tissue and bone sarcoma.

RAD001 is a macrolide, a new derivative of rapamycin. It is orally available and acts as an mTOR inhibitor. TOR is a ubiquitous protein kinase implicated in cell cycle control and specifically in the progression of cells from the G1 to S phase. It is considered to be downstream of PI3-AKT. RAD001 is being developed as an antiproliferative drug with applications as an immunosuppressant and anticancer agent. It is already registered in the transplantation setting as Certican®.

In a phase I study in 33 patients with advanced solid tumors, RAD001 has been given at doses of 20mg, 50mg and 70mg weekly, or 5mg and 10mg daily. Dose limiting toxicities have been stomatitis, neutropenia and hyperglycemia. The recommended dose for further phase II evaluation is 10mg daily (Taberero et al., ASCO 2005, abstract 3007).

2 Study purpose

The purpose of this multicenter, triple-arm, exact binomial single-stage, phase II trial is to determine the preliminary efficacy and safety of RAD001 in patients with histological evidence of progressive or metastatic bone or soft tissue sarcoma.

3 Objectives

Primary objective

- To evaluate preliminary efficacy of RAD001 in progressive or metastatic bone and soft tissue sarcoma (except for GIST). Efficacy is defined as the proportion of patients showing complete response, partial response or stable disease at 16 weeks.

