10.4 Analysis of the primary objective(s)

10.4.1 Variable

The primary variable is defined as the proportion of patients in whom a complete (CR) or partial (PR) response or stable disease (SD) was observed at 16 weeks according to RECIST.

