For simplification, populations for analysis, and the analysis of patient demographics/other baseline characteristics, treatment, primary and secondary efficacy variables, and safety were described without referring to a specific arm. As mentioned above, the methods of analysis were applied to each arm separately.

Changes from the analysis pre-planned in the protocol:

1. Although planned in the protocol, the central radiologic review was only incompletely performed due to a variety of reasons (no images submitted from local to central radiologist, when already the first tumor assessment resulted in an overall lesion response of 'progressive disease'; or images were not assessable according to the central radiologist). An incomplete sequence of central assessments cannot be used to derive the primary and secondary efficacy variables. Thus, the trial will be analyzed based on local tumor assessments only.
2. The intention-to-treat (ITT) set will be used for the primary efficacy analysis rather than the per-protocol (PP) set, since this is what is recommended by RECIST criteria (version 1.0, see [Therasse et al. 2000](#): 'All patients included in the study must be assessed for response to treatment, even if there are major protocol treatment deviations or if they are ineligible. [...] All conclusions should be based on all eligible patients.')

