1.5 Analysis of secondary objectives

1.5.1 Efficacy (secondary)

Secondary efficacy variables were analyzed for the ITT set.

Objective response rate (ORR) was defined as the proportion of patients in whom a complete (CR) or partial (PR) response was observed at Visit 6/Week 16 according to RECIST (version 1.0) based on central radiologic review. Absolute and relative frequencies were presented together with the appropriate exact confidence interval.

Duration of stable disease (CR, PR or SD) applied only to those patients whose best overall response was CR, PR or SD based on local radiologic assessments and was defined as the time from start of treatment to progression or death from underlying disease. Patients not experiencing progression or death at 16 weeks were censored with the date of their last tumor assessment. Duration of response was explored using the Kaplan-Meier method. The Kaplan-Meier estimate for median duration of response as well as the Kaplan-Meier curve was displayed. Although duration of response (CR or PR) was planned to be analyzed within the protocol, this was changed to reach a more valuable analysis since no patient reached a best overall response of CR or PR.

Progression-free survival (PFS) was defined as the time from the date of start of treatment to the date of event defined as the first documented progression or death from any cause. If a patient had not had an event, PFS was censored at the date of the last adequate tumor assessment, which was the date of Visit 6 for the core study phase and the last available tumor assessment for the follow-up phase. PFS was explored by using the Kaplan-Meier method. The Kaplan-Meier estimate for median PFS as well as the Kaplan-Meier curve was displayed.

Time to progression (TTP) was defined as the time from the date of start of treatment to the date of event defined as the first documented progression or death from underlying disease. If a patient had not had an event, TTP was censored at the date of the last adequate tumor assessment, which was the date of Visit 6 for the core phase and the last available tumor

assessment for the follow-up phase. TTP was explored by using the Kaplan-Meier method. The Kaplan-Meier estimate for median TTP as well as the Kaplan-Meier curve was displayed.

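### SAP 1.4.1 scores the primary variable as best overall response, so stable disease at Week 8 followed by radiologic progression at Week 16 counts as success, while the 20% null and 8.9% error are carried over unchanged

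*SAP*

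**What the plan says.** **Protocol.** Section 3 states for each arm: "Efficacy is defined as the proportion of patients showing complete response, partial response or stable disease at 16 weeks". Section 10.4.1 repeats this for the primary variable: "partial (PR) response or stable disease (SD) was observed at 16 weeks according to RECIST". Neither mentions best overall response. BOR is defined only in Post-text supplement 1: "The best overall response is the best response recorded from the start of the treatment until disease progression/recurrence".

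**SAP.** Section 1.4.1 makes the primary variable a BOR of CR, PR or SD, derived from the Week 8 and Week 16 readings by the supplement's rules. Two of them matter here. The rule for stable disease reads "SD = at least one SD assessment > 6 weeks after start of treatment (and not qualifying for CR or PR"), which a single Week 8 scan can meet. The rule for progression is subordinate to it and takes in only patients who have not already met one of the better categories.

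The SAP adds to the PD rule that patients without radiologic progression who leave for unsatisfactory effect, new cancer therapy or death ("from any reason) will be classified as progression") are progressions.

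Sections 1.4.2 and 1.6 apply the decision rules to the BOR count and keep p0 = 20%, p1 = 40% and the 8.9% error. Section 1.6 attributes p0 and p1 to a publication on PFS. Under "Changes from the analysis pre-planned in the protocol" the SAP lists two items, local instead of central reading and ITT instead of PP. The BOR definition is not listed.

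**The concern.** Status at a fixed time and best status over a window are different endpoints. The SAP keeps the phrase about 16 weeks, but its listed rules do not require control at Week 16. One SD reading after more than 6 weeks is enough, which Week 8 satisfies, and progression counts only for patients who have not already qualified. A patient whose disease progresses between the two scans is a failure under the protocol and a success under the SAP.

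This bears directly on the go/no-go decision. SAP 1.5.1 reports that "no patient reached a best overall response of CR or PR", so in the data it describes every counted success comes through the SD rule. Reaching 11 of 36 or 8 of 24 on BOR would not support the protocol's claim about disease control at 16 weeks, and the quoted 8.9% would not be the false-positive rate for that claim.

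**Working it through.** **1. Classify the patient in question.** Take SD at Week 8 and radiologic PD at Week 16.

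| Rule | Result |
|---|---|
| Protocol 3 and 10.4.1: status at 16 weeks | PD, not a success |
| SAP 1.4.1, SD rule: one SD after more than 6 weeks | SD, a success |
| SAP 1.4.1, PD rule: only if not qualifying for CR, PR or SD | does not apply |
| SAP 1.4.1, discontinuation sentence: only without radiologic progression | does not apply |

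For death or clinical discontinuation after a Week 8 SD, the last two rules conflict. One excludes patients who qualify for SD, the other classifies them as progression, and the SAP does not say which prevails.

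**2. Direction.** Almost every Week 16 success is also a BOR success. The one exception under the listed rules is an unconfirmed CR or PR at Week 16 with no usable Week 8 scan, which goes to UNK. BOR therefore in practice adds patients.

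**3. Reproduce the plan's figures.** The inputs n, cut-off r, p0 and p1 are from Table 10-1. The formula is exact binomial, P(X ≥ r | n, p).

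- Arm I: P(X ≥ 11 | 36, 0.20) = 0.0889; P(X ≤ 10 | 36, 0.40) = 0.0904.
- Arm II: P(X ≥ 8 | 24, 0.20) = 0.0892; P(X ≤ 7 | 24, 0.40) = 0.1919.

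These match the stated 8.9%, 9.0% and 19.2%. The arithmetic is right for an endpoint whose null rate is 20%.

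**4. Type I error when BOR exceeds the Week 16 rate.** Let the Week 16 rate be 20% and let q be the share who are SD at Week 8 but have progressed by Week 16. The BOR null rate is p = 0.20 + q. The documents do not give q, so every q below is an assumption.

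| q | p | Arm I, P(X ≥ 11 of 36) | Arm II, P(X ≥ 8 of 24) |
|---|---|---|---|
| 0 | 0.20 | 8.9% | 8.9% |
| 0.02 | 0.22 | 15.0% | 13.8% |
| 0.05 | 0.25 | 27.5% | 23.4% |
| 0.10 | 0.30 | 53.4% | 43.5% |

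- The error equals 10% at p = 0.2042 (arm I) and p = 0.2049 (arm II), so q of about half a percentage point uses up the margin.
- One extra expected patient: p = 0.20 + 1/36 = 0.2278 gives 17.9% in arm I; p = 0.20 + 1/24 = 0.2417 gives 20.5% in arm II.

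**5. An illustration of how large q could be.** Assume a constant hazard. With 20% progression-free at Week 16, the Week 8 rate is √0.20 = 0.4472, so 0.4472 − 0.20 = 0.2472 fail between the scans.

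| Share of those failures scored as SD | p | Arm I | Arm II |
|---|---|---|---|
| one quarter | 0.2618 | 33% | 28% |
| one half | 0.3236 | 65% | 54% |
| all | 0.4472 | 97% | 91% |

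**6. If BOR were kept with an assumed null of 25%.** The smallest cut-offs with error at or below 10% are 13 of 36 (error 9.2%, power at 40% = 73.8%) and 10 of 24 (error 5.5%, power 51.1%).

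**The case against.** **The protocol may have meant BOR.** Sections 7.4 and 10.4.1 refer to RECIST, section 7.4 points to supplement 1, and the supplement's PD and UNK windows run to 16 weeks. The SAP could be spelling out an ambiguous protocol. That bears on intent. A general pointer to RECIST does not turn status at 16 weeks into best status over the window, and the objectives never mention BOR.

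**Unseen sources.** SAP 1.4.3 says the derivation followed a sponsor guideline that is not in the documents. It may settle how death or discontinuation after a Week 8 SD is scored, so that part stays open. The radiologic case is decided by the rules the SAP prints. The PFS publication's time point and rates are also not given, so whether 20% is well founded even for Week 16 cannot be checked here.

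**The size is assumed.** This stands. The upper constant-hazard figures require every interval failure to score as SD, which the discontinuation sentence may prevent for some patients. They are illustrations, not estimates.

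**Early progression is visible elsewhere.** PFS at 16 weeks is a secondary objective and a Kaplan-Meier curve is planned. However, no 16-week point estimate is specified, and the curve does not drive the decision.

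**The remedy may not give exactly 8.9%.** The ITT set need not contain 36 or 24 patients. At p = 0.20, at least 11 of 38 has probability 12.2% and at least 8 of 26 has 13.1%. That is a valid but separate issue.

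**Scope.** The trial is exploratory, and the SAP's statement that there were no CR or PR does not name the arm. Both are true, but arms I and II still carry a formal decision rule.

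**Conclusion.** The concern holds. As written, SAP 1.4.1 counts SD at Week 8 followed by radiologic PD at Week 16 as success, contrary to the protocol's definition. The cut-offs and error rate are applied to that count with no BOR null rate given, and the change is not declared.

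The upward direction follows from the rules. The size depends on an unstated share of patients. The 10% target is passed once that share exceeds about 0.4 percentage points in arm I or 0.5 in arm II, and a share of 5 points gives an error of 27.5% or 23.4%. These figures assume a true Week 16 rate of 20% for an inactive drug and exactly 36 and 24 patients. Arm III is not affected, because protocol section 10 makes it descriptive. This must be fixed before the decision rules are applied.

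**What to change.** In SAP 1.4.1:

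- Define a responder as CR, PR or SD at the Visit 6/Week 16 assessment with no earlier progression or death.
- Count progression or death by Week 16, and missing or unknown Week 16 status, as non-response.
- Apply 11 of 36 and 8 of 24 to that count in arms I and II.
- Report BOR as supportive, list its definition among the changes from the protocol, and state which rule prevails for death or discontinuation after a Week 8 SD.

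In SAP 1.5.1, add the 16-week Kaplan-Meier PFS estimate with an 80% confidence interval.

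The cost is SAP wording and one flag re-derived from scans the protocol already schedules. The drawback is a lower reported response rate.

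If BOR is to stay primary, justify p0 and p1 for BOR, recompute sample size and cut-offs, and do not cite 8.9% as the error for 16-week disease control. That costs more: under the assumed 25% null, power at the present sample sizes falls from 91% to 74% in arm I and from 81% to 51% in arm II.
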